3 INVESTIGATION POPULATION AND INVESTIGATION PROCEDURES

3.1 Inclusion and exclusion criteria, justification of Investigation population

For this study, n=45 subjects will be recruited

Inclusion Criteria

- Young, healthy adults between the ages of 18 and 30
- No surgical interventions on the musculoskeletal system in the trunk area and lower extremities

Exclusion criteria

- Current pain conditions
- Current inflammatory states
- Medication intake (excl. anticonception drugs)
- Pregnant subjects
- Athletes
- Children/adolescents
- Non-intact skin conditions (e.g. psoriasis)
- Known circulatory disorders
- Cold allergy (Raynaud's syndrome)

3.2 Recruitment, screening and informed consent procedure

Participants are recruited via the websites of the Thim van der Laan (www.physioschule.ch) physiotherapy schools and the SUPSI (www.supsi-landquart.ch University of Applied Sciences and Arts Southern Switzerland). An electronic advertisement is placed on the screens in the building of Thim van der Laan AG in Landquart. The ad texts are based on the guidelines of the Ethics Committee of the Canton of Zurich.

The initial contact is made directly with the head of studies in the research laboratory of the University of Applied Sciences and Arts Southern Switzerland. At the first contact, the potential participants are informed about the procedure and the risks of the examination, as well as about the conditions and the amount of compensation.

The principal investigator will explain to each participant the nature of the study, its purpose, the procedures involved, the expected duration, the possible risks and benefits, and any inconveniences it may entail. Each participant is informed that participation in the examination is voluntary and that he or she can withdraw from the examination at any time and that withdrawing consent will not affect his or her subsequent supervision.

The study leader then hands over the subject information and the declaration of consent. In the subject information there is a checklist that the potential test persons must fill out. This checklist checks whether the potential test subjects are suitable for the examination. The test subjects are told that they can contact us at any time if questions arise.

The completed checklist and the signed consent form will be handed over to the Director of Studies and checked by him. If all exclusion criteria are checked and the consent form is signed

and the subject has no more questions, he/she is admitted to the examination. A copy of the signed informed consent form will be given to the study participant. The declaration of consent is kept as part of the study documents. The original of the signed consent form is kept as a study document in a locked filing cabinet.

After successful completion of the intervention, the participants receive a remuneration of 50 Swiss francs.

3.3 Investigation procedures

Investigation duration:

Subject to EC approval in 2024.

Recruitment period: January 2025

Conduct of the study: February - March 2025

Statistics and writing of the article: April – July 2025

Individual Investigation duration for each participant

Phase	Content	Time
Recruitment	Handing out patient information & consent, explanation of the experiment	30 min
Experiment Day 1	Anthropometry, baseline measurement, muscle soreness protocol (cooling: group A)	60 min
Experiment Day 2	Follow-up measurement 24 hours (Cooling: Group A and Group B)	30 min
Experiment Day 3	Follow-up measurement 48 hours (Cooling: Group A and Group B)	30 min
Experiment Day 4	Follow-up measurement 72 hours (Cooling: Group A and Group B)	30 min
Total time required per subject		180 min

Recruitment

As soon as the potential test subjects show interest in the study and arrive at the laboratory in Landquart, they are sent to the study director. If he is not present or available at that time, interested parties are asked to appear on another day.

The head of the study explains the procedure, the tests carried out, the risks and possible inconveniences. In addition, it is explained that participation is voluntary and that withdrawal is possible at any time, without giving reasons, without this having a negative impact on future care. The test subjects then receive the test subject information, which describes the examination in detail and in an understandable way. The document also contains a checklist that must be completed. The declaration of consent is also provided and must be signed and returned by the Director of Studies before the start of the programme. The doctor checks the completed checklist and confirms the consent.

Baseline measurements

The room temperature and relative humidity are determined at the beginning of each measurement day (Voltcraft MT52 digital multimeter, Hirschau, Germany). Baseline measurements include demographic data (age, gender, height). Anthropometric features at the beginning of the study included height (GPM Stadiometer, Zurich, Switzerland), body mass, and body fat percentage estimation. Body mass and lower body fat percentage were measured using

a TANITA-TBF 611 scale (Tokyo, Japan). The estimate of the percentage of lower body fat was chosen because the cold pack was applied to the thigh, which mainly affects the lower extremities. Recovery parameters (see Exact Measurement Method and Primary and Secondary Endpoints) are assessed in the same order for each measurement: (1) Inflammation Scores, (2) Muscle Swelling, (3) Soreness, (4) Maximum Voluntary Isosomic Muscle Contraction. The measurement method and the equipment used for each specific result are described in Chapter 3.2.

Randomization

The randomization of the subjects will take place on the day of the baseline measurement by drawing a lot. It is ensured that the same number of tickets are available for each intervention group (5 tickets per group) and test subjects. If the number of subjects in a group exceeds one third of the total number of subjects, the lots of this group will be removed. In order to ensure the equality of the groups in terms of covariates and gender, the composition of the groups is monitored. As soon as half of a group consists of male or female subjects, the tickets for this group are removed for future subjects of the same sex.

The tickets are made of folded paper with the numbers 1, 2 or 3 on them and are placed together in a container. The drawing of the lots is carried out by the test persons themselves. After the draw, the subjects hand over the unread ticket to the study director, who assigns them to a group.

Blinding

Since cold applications are tested in this study, blinding is not possible.

Sore muscle protocol

To induce muscle soreness, a one-legged knee extensor protocol is used, which has already been used (Ruas et al., 2022). Participants will be instructed to straighten and bend their knee for 6 sets for 12 – 15 reps, with 2 minutes rest between sets. During the 2-minute break, the participants are allowed to sit on the chair. The execution of the knee extensor protocol is visually observed by an examiner. Verbal corrections of the execution can be given by the examiner. However, no verbal encouragement is given. All training sessions are carried out in the morning. If a participant is unable to perform all the repetitions of a set due to extreme fatigue or maximum effort, the set can be stopped and a new set can be started after the rest period. However, at least 12 repetitions per set must be performed. Otherwise, this will be considered an abandonment.

Intervention

The subjects in group A (immediate cooling) receive the first cooling on the two thighs immediately after the end of the muscle soreness protocol. This cooling is carried out in the supine position. After this application, you can leave the laboratory and the measurement of the skin temperature is stopped.

Group B (delayed cooling) and group C (control group) do not receive any cooling (group B) or any intervention (group C) immediately after the muscle soreness protocol. However, you will also need to spend 20 minutes lying on your back in the lab before the skin temperature measurement is completed.

Follow-up measurements

Follow-up measurements will be taken for each measurement in the same order as for the baseline measurement ((1) Inflammatory markers, (2) Muscle swelling, (3) Soreness of muscles, (4) Maximum voluntary isometric contraction). The follow-up measurements take place 24, 48, and 72 hours after the muscle soreness protocol in the laboratory in Landquart.

The measurement method and the equipment used for each specific result are described in Chapter 3.2.

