Investigation procedures	
Subject recruitment
 
The test subjects are recruited at the University of Physiotherapy THIM in Landquart and the University of Applied Sciences and Arts Southern Switzerland in Landquart.
 
The subject information and the declaration of consent are given to the test subjects. In the subject information there is a checklist that the test persons must fill out in order to check the inclusion and exclusion criteria.
 
If the subjects agree with the information, have completed the checklist and signed the consent, they will be summoned to make an appointment for the measurement.
 
Investigation Protocol
 
As soon as the signed consent of the test person has been received and an appointment has been made, the following procedure is followed. The anthropometric data of the subjects will be collected and group randomization will be carried out. Afterwards, the baseline measurements are carried out and the measurement of the skin temperature is started. Then the muscle soreness protocol (6 x 12 to 15 one-legged knee extensor protocol with a 2-minute break between sets) is completed. Cooling group A then receives the first 20-minute cooling of the thigh group.
 
Cooling group B and the control group leave the laboratory 20 minutes after the muscle soreness protocol. The measurement of skin temperature is stopped within all groups 20 minutes after the muscle soreness protocol.
 
Cooling group B begins cooling the thigh muscles 24 hours after the muscle soreness protocol. Both cooling groups perform cooling of the thigh muscles 3 x / day for the duration of the data collection (up to 72 hours according to the muscle soreness protocol).
 
At intervals of 24, 48 and 72 hours, the primary endpoints of the study are collected again. These include: muscle soreness, inflammation levels, muscle swelling, maximum voluntary isometric contraction of the thigh muscles.
 
Measurement of sore muscles
 
The level of ventrally felt muscle soreness symptoms is measured using a VAS scale (0 – 10 cm). The test subjects rate the perceived muscle soreness in both ventral thighs in a 90° knee flexion position. The measurement takes place during the baseline measurement and, 24 hours, 48 hours and 72 hours after the intervention.
 
Inflammation levels
 
The inflammation values (blood sedimentation rate, C-reactive protein, creatine kinase) are determined by venous blood sampling. The measurement takes place during the baseline measurement and, 24 hours, 48 hours and 72 hours after the intervention.
 
Muscle swelling
 
The measurement of muscle swelling of the quadriceps femoris muscle is carried out by ultrasound measurement. The measurement is carried out in a resting position and a cross-section of the muscle is recorded. The measurement takes place during the baseline measurement and, 24 hours, 48 hours and 72 hours after the intervention.
 
Measurement of maximum voluntary isometric thigh muscle contraction (MVIC)
 
MVIC is performed on an ergometer chair for biomechanical measurements and is given in kg. The measurement takes place during the baseline measurement and, 24 hours, 48 hours and 72 hours after the intervention.
 
Surface temperature
 
The surface temperature is measured using the iButton system. These sensors are glued to the skin for the duration of the measurement. The button sensors store the current temperature information and can then be read out via a computer. These measurements are started during the baseline survey, for the duration of the muscle soreness protocol, and up to 20 minutes after the muscle soreness protocol.
 
Detection of thermal perception
 
The thermal perception of the participants is recorded immediately after exposure to cold using the standardized Thermal Perception Scale (-4 to +4). This scale ranges from -4 ("extremely cold") to +4 ("extremely warm"), with 0 being considered neutral. The evaluation is carried out

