δ_i	The difference between the i th treatment agent and the control agent ($\mu_i - \mu_c$) for which the test strength is calculated.
σ	The standard deviation of the responses within each group.
Alpha	The probability of rejecting the null hypothesis that the control mean is equal to the treatment mean described in this row.

Summary statements

A parallel 3-group design (with a control group and 2 treatment groups) is used to test whether the mean for each treatment group is different from the mean of the control group ($H_0: \delta = 0$ versus $H_1: \delta \neq 0, \delta = \mu_i - \mu_c$). The hypotheses are evaluated using two two-sided, two-sample methods. Bonferroni-adjusted t-tests with the same variance and an overall (experimental) Type I error rate (α) of 0.05. The common standard deviation for all groups is assumed to be 2.1. The mean value of the control group is assumed to be 4.72. The treatment means 2.21 and 1.87 with at least 80% test strength to be detected in each case. For the test, the (same) group sample size needed for each of the three groups (control and treatments) is 13 (39 subjects in total). The group sample sizes were calculated using PASS 2023, version 23.0.1.

Sample size taking into account the dropout rate

Group	Dropouts Abandonment Rate	Number of cases/group	Number of cases with drop-out rate	Number of abandoned participants
1 - 3	10%	13	15	2
Total	n/a	39	45	6

Taking into account the drop-out rate

Taking into account a dropout rate of 10%, the group sizes in each study arm should be 15 subjects.

Statistical approach to examine the primary endpoints

The statistical analysis is performed using IBM SPSS Statistics (version 27, IBM Corp., Armonk, NY, USA) and the significance level is set to $p < 0.05$.

In order to be able to determine the differences between groups, a repeated ANOVA analysis is carried out with a factor of 1: time (baseline, 24 hours, 48 hours, 72 hours) and a factor of 2:

intervention (group A, group B, group C) for the recovery parameters (inflammation values, muscle swelling, muscle soreness data, maximum voluntary isometric muscle contraction).

The examination is discontinued if the participants are intolerant to the local cold application. Participants in the IC and DC groups are instructed to cancel a cooling session and contact their contact immediately if they experience symptoms such as severe pain/discomfort as a result of the cooling.

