4.2. Handling of missing data and drop-outs

Missing data, missed training sessions or abandonments are noted in the CRF. Data from patients who discontinue the examination is collected and stored. Drop-outs are not replaced by the recruitment of new participants. If consent is withdrawn, the data already collected will be included in the analysis for scientific and safety reasons. These are only anonymised after the analysis (Art. 32 ClinO-MD).

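### The lot is drawn before baseline and exercise, so a subject who fails the 12-repetition rule is lost after randomisation, without replacement and from the two-per-arm dropout allowance

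*Combined protocol and SAP*

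**What the plan says.** **Order of events.** The investigation protocol in the Synopsis puts allocation ahead of every measurement: "group randomization will be carried out. Afterwards, the baseline measurements are carried out". The exercise comes next: "Then the muscle soreness protocol (6 x 12 to 15 one-legged knee extensor protocol with a 2-minute break between sets) is completed". Section 3.3 (Randomization) places the draw on the baseline day without fixing its position. The subject hands an unread ticket to the study director, who assigns the group.

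**Exercise rule.** Section 3.3 (Sore muscle protocol) asks subjects to "straighten and bend their knee for 6 sets for 12 – 15 reps, with 2 minutes rest between sets". If fatigue prevents completion of a set, "the set can be stopped and a new set can be started after the rest period". The next sentences read: "However, at least 12 repetitions per set must be performed. Otherwise, this will be considered an abandonment".

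**Losses.** Section 4.2: "Drop-outs are not replaced by the recruitment of new participants". Section 4.1: "Taking into account a dropout rate of 10%, the group sizes in each study arm should be 15 subjects". The table above that sentence uses the term abandonment for dropout and shows 13 raised to 15 per arm, with 2 abandoned participants per arm and 6 in total.

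**Not stated.** The documents do not say what failure rate is expected, who declares an abandonment, whether that person knows the group, whether such a subject attends the 24, 48 and 72 h visits, or which analysis set applies.

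**The concern.** All three groups are treated alike until the exercise ends. Whether a subject can complete it could therefore be known before a group is assigned. By drawing first, the plan turns a failed run-in into a loss after randomisation, which cannot be refilled and which competes with withdrawal, illness and cold intolerance for two places per arm.

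The planned analysis is a repeated-measures ANOVA over baseline, 24, 48 and 72 h. In its usual complete-case form, a subject with baseline data only contributes nothing, and no missing-data method is given to change that.

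The early draw also means that at least the study director knows the allocation while baseline soreness and strength are measured and the exercise is performed. Drawing later would avoid this in a trial that cannot be blinded.

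**Working it through.** **Inputs (section 4.1).** Control mean 4.72; treatment means 2.21 (A) and 1.87 (B), so differences of 2.51 and 2.85; SD 2.1; two-sided alpha 0.05 per comparison with no correction, as in the calculation table; 13 evaluable per arm; 10% dropout; 15 per arm. The accompanying text calls the tests Bonferroni-adjusted. That mismatch is a separate matter, and the uncorrected alpha is used here because it reproduces the plan's power.

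**Step 1: reproduce the plan.** Two-sample t-test with equal variances, noncentrality = difference / (SD × √(2/n)). At n = 13 the denominator is 2.1 × √(2/13) = 0.824. The noncentrality is 2.51/0.824 = 3.05 for A and 2.85/0.824 = 3.46 for B, with 24 degrees of freedom. Power is 0.83233 and 0.91287, exactly as tabulated. For dropout, 13/0.9 = 14.4, rounded up to 15, so the allowance is 15 − 13 = 2 per arm.

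**Step 2: power as evaluable numbers fall** (same number in both compared arms).

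| Evaluable per arm | A vs control | B vs control |
|---|---|---|
| 13 | 0.832 | 0.913 |
| 12 | 0.799 | 0.888 |
| 11 | 0.760 | 0.857 |

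If only one of the two compared arms falls to 12, power lies between the first two rows.

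**Step 3: chance of exceeding the allowance through exercise failure alone.** The share of subjects failing, p, is an assumption. For one arm, P(X ≥ 3) with X ~ Binomial(15, p); for at least one of three arms, 1 − (1 − P)³.

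| Assumed p | One arm loses 3 or more | At least one of three arms |
|---|---|---|
| 1% | 0.0004 | 0.001 |
| 2% | 0.003 | 0.009 |
| 5% | 0.036 | 0.10 |
| 10% | 0.184 | 0.46 |

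**Step 4: exercise failure on top of the planned 10%.** Expected completers per arm from 15 are 15 × 0.9 = 13.5 with no exercise failure, 15 × 0.95 × 0.9 = 12.8 at 5%, and 15 × 0.9 × 0.9 = 12.2 at 10%. To keep 13, the plan would need 13/(0.95 × 0.9) = 15.2, so 16 per arm, or 13/(0.9 × 0.9) = 16.05, so 17 per arm.

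**The case against.** **The allowance already covers abandonment.** The section 4.1 table budgets for it by name, and losing exactly two per arm leaves the planned 83% and 91% power. This stands. It is the third loss in an arm that matters, and one further loss in each arm takes A only to 0.799.

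**One short set may not end participation.** A reader might infer that 11 repetitions in any one of six sets is fatal. The preceding sentence lets a fatigued subject stop a set and begin another after the rest, and does not say whether the new set stands in for the stopped one. The strict reading is possible, but the text does not settle it.

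**Abandoned subjects are not said to be removed.** Section 4.2 keeps the data of those who discontinue, and section 3.4 does not list short sets as a reason for exclusion. Removal is the likely practical result of a complete-case ANOVA, not a stated rule.

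**Bias between arms is not shown.** A reader might infer that an unblinded examiner can drop subjects by group, or that the rule trims those who would become sorest. The failure precedes all cooling and so cannot be a cooling effect. No section says that the examiner watching the exercise knows the group, and a repetition count is fairly objective. Nothing in the documents links early fatigue to later soreness.

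**The failure rate is unknown.** It is tempting to argue that six sets multiply a small risk: 1 − (1 − 0.0174)⁶ = 0.10, so a 1.7% failure rate per set would cost 10% of subjects. That assumes independent sets. Failures that cluster within tired subjects would bring the loss down, to as little as 1.7% at the same per-set rate.

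What survives is the order of events, the ban on replacement and the shared allowance.

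**Conclusion.** The point holds as an inexpensive design improvement, not as a demonstrated bias or a demonstrated loss of power. Followed as written, the plan can lose allocated subjects on Day 1 for a reason that could have been settled before allocation. It also leaves the group known to at least the study director through baseline and exercise.

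The size depends entirely on an exercise-failure rate that the documents do not give. At 1–2% of subjects the effect is negligible. At 5–10%, the chance that at least one arm exceeds its allowance from this cause alone runs from 0.10 to 0.46. The comparison of A with control is the more exposed, because 12 per arm already falls just below the 80% target; B stays above 0.85 even at 11. These figures assume independent failures between subjects, the same rate in each arm, abandoned subjects contributing nothing to the analysis, and the plan's own means, SD and uncorrected alpha.

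**What to change.** **Preferred.** In the Synopsis (investigation protocol) and section 3.3 (Randomization), place the draw after baseline and after the exercise protocol is completed, immediately before the first cooling or the 20-minute rest. State that a subject who does not complete the exercise is recorded as not randomised, is not a drop-out under section 4.2, and may be refilled until 45 have been randomised.

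**Cost.** A wording change, possibly a few more subjects screened, and a short draw just before cooling. Frozen packs would have to be ready at every session, since the group is not known until then.

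**If the draw stays first.** Record repetitions per set in the CRF. Keep drawn subjects in their allocated group, measure them at 24, 48 and 72 h where safety allows, and analyse them as randomised. Report full completers as a sensitivity analysis. The cost is one CRF line and some subjects with a smaller exercise stimulus in the main analysis, which may dilute the effect slightly.

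**In either case.** Reconcile the sentence in section 3.3 that lets a stopped set be followed by a new one with the sentence that makes fewer than 12 repetitions an abandonment, and say who makes that call.
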